Appendix B.	Technical Detail and Supplemental Information Regarding Statistical Procedures and Programs.....	25
Appendix C.	Reference Values/Toxicity Grades	28
Appendix D.	Concomitant Medications	29

Table of Abbreviations

Abbreviation or Term	Definition/Explanation
AFT	Accelerated Failure Time Model
ANOVA	Analysis of Variance
ANCOVA	Analysis of Covariance
CI	Confidence Interval
CRF	Case Report Form
C-SSRS	Columbia-Suicide Severity Rating Scale
CTCAE	Common Toxicity Criteria for Adverse Events
DMC	Data Monitoring Committee
DMP	Data Management Plan
DRE	Disease Related Event
DTP	Data Transfer Plan
EAS	Efficacy Analysis Set
ECG	Electrocardiograph
EOS	End Of Study
ETT	Exercise Treadmill Test
ETT _r	Exercise Treadmill Test post-randomization
FAS	Full Analysis Set
HR	Heart Rate
IP	Investigational Product
MedDRA	Medical Dictionary for Regulatory Activities
NCI	National Cancer Institute
SAE	Serious Adverse Event
SAP	Statistical Analysis Plan
SBP	Systolic Blood Pressure
TEAE	Treatment Emergent Adverse Event
TET	Total Exercise Time
ULN	Upper Limit of Normal
VHP	Voluntary Harmonization Procedure

1. Introduction

The purpose of this Statistical Analysis Plan (SAP) is to provide details of the statistical analyses that have been outlined within Protocol Amendments 4 and associated Country Specific Supplement 3 for AMG 334 Study 20140254 dated 28 October 2016 and 14 November 2016, respectively. The scope of this plan includes the primary and final analyses that are planned and will be executed by the Biostatistics department unless otherwise specified.

2. Objectives

2.1 Primary

To evaluate the effect of AMG 334 compared to placebo on exercise capacity in subjects with stable angina as measured by total exercise time (TET) during an exercise treadmill test (ETT).

2.2 Secondary

To evaluate the effect of AMG 334 compared to placebo during an ETT on the time to the onset of:

- Exercise-induced angina
- ST-segment depression

2.3 Safety

To evaluate the safety and tolerability of AMG 334 in a population with stable angina.

3. Study Overview

3.1 Study Design

This is a phase 2a, multicenter, randomized, double-blind, placebo-controlled study in subjects with stable angina. At least 54 subjects will be randomized in a 1:1 ratio to receive either a single dose of AMG 334 140 mg or placebo intravenously prior to completing an ETT. Randomization will be stratified by the TET average of the 2 qualifying screening ETTs (< 7 minutes or ≥ 7 minutes). Treatment group will be blinded to the investigator, subjects, and the Amgen study team.

3.2 Sample Size

The primary endpoint is the change from baseline in TET. Assuming between-subject standard deviation for change from baseline in exercise duration of 130 seconds, with a planned study size of at least 27 subjects in each group and a difference in change from baseline in exercise duration of 0 seconds between AMG 334 group and placebo group, there is an 80% probability (power) that the lower bound of the 90% confidence interval

(CI) will exceed -90 seconds. A margin larger than -60 seconds between groups was required to accommodate the possibility of more than 60 second (up to 20%) difference allowed in qualifying TETs for individual subjects. Because of this within-subject TET variation, a maximum TET difference of 90 seconds between the AMG 334 group and placebo group was considered reasonable in this study. A margin of -90 seconds was selected, which corresponds to the margin used in previous study testing a comparable hypothesis (Patterson, et.al 2005). Twenty-nine subjects are needed in each group if considering 5% dropout.

When approximately 45 subjects have been enrolled, Amgen may conduct a blinded sample size-estimation and may choose to alter the sample size based on the blinded variance in the pooled treatment groups.

4. Study Endpoints and Covariates

4.1 Study Endpoints

4.1.1 Primary Endpoint

- Change from baseline in TET

4.1.2 Secondary Endpoints

- During the ETT
 - Time to onset of exercise-induced angina
 - Time to onset of ≥ 1 mm ST-segment depression

4.1.3 Safety Endpoints

- Adverse events and disease related events
- Changes in vital signs

For Country Specific Supplement countries only:

- Maximum change in ST-segment depression (mm) from baseline
- Maximum heart rate (HR)
- Maximum change in systolic blood pressure (SBP) from baseline

4.2 Planned Covariates

The stratification factor of baseline TET (< 7 or ≥ 7 minutes) will be included as a covariate in the primary analysis of the efficacy endpoints.

Stratification factor will use the values used for randomization unless otherwise noted.

5. Hypotheses

The primary endpoint of the study will be tested for AMG 334 compared to placebo, with type I error 0.1

- Null Hypothesis: In subjects with angina, AMG 334 does significantly decrease exercise capacity (by at least 90 seconds), as measured by change from baseline in total exercise time, compared to placebo, and that the true treatment difference in change from baseline in TET is -90 seconds or more (worse).
- Alternative Hypothesis: In subjects with angina, AMG334 does not decrease exercise capacity, as measured by change from baseline in total exercise time, compared to placebo, and that the difference in change from baseline in TET if any, is less than a 90 second decrease.

6. Definitions

6.1 Study Dates

Enrollment Date

Enrollment Date is defined as the randomization date.

Randomization Date

Randomization Date is defined as the date subject was allocated to a treatment group.

First IP Dose Date

First IP Dose Date is the date on which a subject is administered the first dose of IP following randomization. For subjects who are randomized but not dosed with IP, first dose date is missing.

Subject-level End of Study (EOS) Date

End of study for each subject is defined as the last date on which the subject last completed a protocol-specified procedure. The date will be recorded on the End of Study CRF page.

Primary Completion Date

The primary completion date is defined as the date the last subject completes the on study ETT

Study Completion Date

The study completion date is the EOS date of the last subject in the study.

6.2 Study Points of Reference

Study Day 1

Study Day 1 is defined as the first IP dose date. For subjects who are randomized but not dosed, Study Day 1 is defined as the date of randomization.

Study Day

Study Day is defined as the number of days from Study Day 1.

Before Study Day 1:

$$\text{Study Day} = (\text{Date of Interest} - \text{Date of Study Day 1})$$

On or after Study Day 1:

$$\text{Study Day} = (\text{Date of Interest} - \text{Date of Study Day 1}) + 1$$

Therefore the day prior to Study Day 1 is -1.

Post-baseline Study Visit

See [Appendix A](#).

Completing Study

A subject is defined as completing study if the primary reason for ending study is "Completed".

Completing Investigational Product (IP)

A subject is defined as completing IP if the reason for ending IP is "Completed".

6.3 Baseline and Demographics

Age at Enrollment

Subject age at enrollment will be collected in years in the clinical database.

Baseline Values

Baseline TET is the average of the 2 qualifying screening ETTs.

If subject completes Columbia-Suicide Severity Rating Scale (C-SSRS) form on Study Day 1 then all individual items from Study Day 1 visit will be used as baseline. If subject does not complete C-SSRS form on Study Day 1 then the last completed form prior to Study Day 1 will be used.

For all other variables, unless otherwise specified, baseline values are defined as the last non-missing value before the first dose of IP, or randomization date for subjects who never received IP. In cases where baseline measurements are taken on the same day as the first IP dose date, it will be assumed that these measurements are taken prior to IP being administered.

BMI

Subject's BMI will be derived in kg/m² in the clinical database.

6.4 Efficacy Endpoints

Change from baseline in TET

Change from baseline in TET = TET from on-study ETT post-randomization -
baseline TET

Time to Event

Time to event (onset of angina, ≥ 1 mm ST-segment depression) is defined as the time subject received IP to the time of event onset.

Time to event = event onset time – time received investigational product

If no event occurs, then subject will be censored at the ETT stop time.

6.5 Safety Endpoints

Treatment-Emergent Adverse Event

Events categorized as adverse events (AEs) starting on or after first dose of IP as determined by the flag indicating if the AEs started prior to the first dose on the Events CRF and up to and including 84 days after the end of IP or end of study, whichever comes first.

Serious adverse events (SAEs) are events categorized as AEs that are starting on or after first dose of IP as determined by the flag indicating if the adverse event started prior to the first dose of the Events CRF and up to and including 84 days after the end of investigational product.

Treatment-emergent Disease-related Event

Events categorized as Disease-related Events (DREs) starting on or after first dose of investigational product as determined by the flag indicated if the event started prior to the first dose on the Events CRF and up to and including 84 days after the end of investigational product.

Serious disease-related events are events are events categorized as DREs that are starting on or after first dose of investigational product as determined by the flag indicating if the event started prior to the first dose on the Events CRF and up to and including 84 days after the end of investigational product

Maximum Change from Baseline in SBP

The maximum change from baseline in SBP is calculated by the maximum value of (SBP after first dose date— baseline SBP)

Maximum Change from Baseline in HR

The maximum change from baseline in HR is calculated by the maximum value of (HR after first dose date – baseline HR)

Maximum Change from Baseline in ST-Segment Depression

The maximum change from baseline in ST-Segment Depression is calculated by the maximum value of (ST-Segment Depression after first dose— baseline ST-Segment Depression).

Columbia-Suicide Severity Rating Scale (C-SSRS)

The C-SSRS is a clinician rating of suicidal behavior and ideation. Two versions depending on the type of visits will be used in this study: Screening and Since Last Visit. The C-SSRS consists of a maximum of 20 items to evaluate suicidal behavior and suicidal ideation.

7. Analysis Subsets

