## 9.2.2 Adverse Events

### 9.2.2.1 Reporting Procedures for Adverse Events That do not Meet Serious Criteria

The investigator is responsible for ensuring that all adverse events observed by the investigator or reported by the subject that occur after first dose of investigational products through the end of study period (12 weeks after the last dose of IP) are reported using the Event CRF.

The investigator must assign the following adverse event attributes:

- Adverse event diagnosis or syndrome(s), if known (if not known, signs or symptoms),
- Dates of onset and resolution (if resolved),
- Severity
- Assessment of relatedness to investigational product(s) and/or any study-mandated activity or procedure, and
- Action taken.

The adverse event grading scale used will be the Common Terminology Criteria for Adverse Events (CTCAE). The grading scale used in this study is described in [Appendix A](#).

The investigator must assess whether the adverse event is possibly related to the investigational products. This relationship is indicated by a “yes” or “no” response to the question: Is there a reasonable possibility that the event may have been caused by the investigational medicinal products?

The investigator must assess whether the adverse event is possibly related to any study-mandated activity (eg, administration of investigational product, protocol-required therapies, device(s) and/or procedure (including any screening procedure(s)). This relationship is indicated by a “yes” or “no” response to the question: “Is there a reasonable possibility that the event may have been caused by a study activity (eg, administration of investigational product, protocol-required therapies, device(s)), and/or procedure”?

If the severity of an adverse event changes from the date of onset to the date of resolution, record as a single event with the worst severity on the Adverse Event Summary CRF.

---

CONFIDENTIAL

**AMGEN**®

---

**AMGEN**®

---

Product: Erenumab (AMG 334)  
Protocol Number: 20140254  
Date: 28 October 2016

Page 41 of 63

---

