#### **12.4 Investigator Responsibilities for Data Collection**

The investigator is responsible for complying with the requirements for all assessments and data collection (including subjects not receiving protocol-required therapies) as stipulated in the protocol for each subject in the study. For subjects who withdraw prior to completion of all protocol-required visits and are unable or unwilling to continue the Schedule of Assessments (Table 1), the investigator can search publically available records (where permitted) to ascertain survival status. This ensures that the data set(s) produced as an outcome of the study is/are as comprehensive as possible.

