Appendix A. Post-baseline Study Visits

Since the actual visit for a subject may not exactly coincide with their targeted visit date, the actual visit date is mapped to the study visit as following. The study day window will be utilized to define study visit for labs, antibody, vital signs and physical measurements collected at office visits.

Study Visit	Target Day	Study Day
Week 4	29	16-43
Week 8	57	44-71
Week 12	85	72 to Min (EOS Date, last IP dose date + 84 days)

Note:

1. If more than one visit (including unscheduled visits, ie, CPEVENT = 'UNSCHED') fall within the same defined window, scheduled visit will be used regardless of the distance from the target day. Unscheduled visit will only be used when there is no scheduled visit in the defined window. The closest visit to the target day among the same type of visit (scheduled vs. unscheduled) will be considered for analysis. If two assessment dates are equidistant from the target date, the latter visit will be considered for analysis.
2. For Country Specific Supplement countries, CSSRS and ECG data are collected at week 2 (target day 14), corresponding to study day 1-28.

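### SAP 6.5 cuts the TEAE window at a subject's end of study but not the SAE window, so an SAE after an early end of study can be in the SAE table and missing from the all-TEAE table

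*SAP*

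**What the plan says.** SAP 6.5 sets the upper end of each safety window.

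- **TEAEs:** "up to and including 84 days after the end of IP or end of study, whichever comes first".
- **SAEs**, in the next paragraph under the same heading: "started prior to the first dose of the Events CRF and up to and including 84 days after the end of investigational product". There is no end-of-study limit.
- **Treatment-emergent DREs and serious DREs:** also 84 days after product, with no end-of-study limit.

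SAP 6.1 makes end of study a subject-level date: "End of study for each subject is defined as the last date on which the subject last completed a protocol-specified procedure". SAP 10.6.1 then summarises all TEAEs, serious AEs, AEs leading to withdrawal of product and fatal AEs as separate items. SAP 6.5 gives no window for the fatal-AE table.

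The protocol uses one reporting period for every category. Protocol 9.2.2.1 has non-serious events reported "after first dose of investigational products through the end of study period (12 weeks after the last dose of IP"), and Protocol 9.2.1 (DREs) and 9.2.2.2 (SAEs) also end 12 weeks after the last dose. SAP section 11 declares no change from the protocol-specified analyses, and nothing in the SAP explains why one category is cut shorter.

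**The concern.** A reader of a safety report expects every treatment-emergent SAE to be among the treatment-emergent AEs. Under the two definitions as written, that can fail for a subject whose end of study comes before Day 85. A serious event starting between those two dates meets the SAE definition and fails the TEAE definition. The SAE table could then show a subject or a preferred term that the all-TEAE table does not. With about 27 subjects per arm, one such case is visible in the incidence. Programmers who resolve the difference in different ways would also report different TEAE counts from the same data.

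**Working it through.** **Inputs**

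- Window length: 84 days after end of product (SAP 6.5), which is the protocol's 12 weeks: 12 × 7 = 84.
- Dosing: a single infusion on Study Day 1 (Protocol 6.2.1.1).
- Day numbering: Study Day = date − Day 1 date + 1, from Day 1 on (SAP 6.2).
- Week 12 target: Day 85 (SAP Appendix A). Visit window: ± 1 week (Protocol Table 1 footnote), so Day 78 to Day 92.
- Planned arm size: 27 (SAP 3.2).

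**Reproducing the plan's figure.** The last day of an 84-day window after a Day 1 dose is 1 + 84 = Day 85, which equals the Week 12 target day.

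**Gap between the windows**

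- TEAE end = min(end-of-study day, 85)
- SAE end = 85
- Gap = 85 − min(end-of-study day, 85)

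| End-of-study day | TEAE end | SAE end | Gap (days) |
|---|---|---|---|
| 1 | 1 | 85 | 84 |
| 15 | 15 | 85 | 70 |
| 29 | 29 | 85 | 56 |
| 57 | 57 | 85 | 28 |
| 71 | 71 | 85 | 14 |
| 78 | 78 | 85 | 7 |
| 84 | 84 | 85 | 1 |
| 85 or later | 85 | 85 | 0 |

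For exit on Day 29 the TEAE window loses 56/84 = 67% of its length. The rows for Day 78 and Day 84 are completers whose Week 12 visit fell early within its permitted window, so the gap is not confined to early leavers.

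**The other reading of the TEAE clause.** The phrase could mean 84 days after whichever is earlier, end of product or end of study. Product ends on Day 1 and end of study cannot be earlier for a dosed subject, so this gives min(1, end-of-study day) + 84 = 85 for everyone and no gap. On that reading the clause has no effect in this trial. SAP Appendix A ends the Week 12 window at "72 to Min (EOS Date, last IP dose date + 84 days"), which is the minimum-of-two-dates rule and supports the reading used in the table.

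**Effect of one case.** A subject whose only adverse event is an SAE in the gap is missing from the TEAE numerator: 1/27 = 3.7 percentage points in that arm. If the subject has another TEAE inside the window, overall TEAE incidence does not move and only the row for that event is short by one.

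**After harmonising.** With a single end rule, either Day 85 for all or min(end-of-study day, 85) for all, the gap is 0 for every end-of-study day and every tabulated SAE is also a TEAE.

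**The case against.** The strongest reply is that the case will hardly arise. Protocol 7.3.10 has events recorded through end of study, and Table 1 ends recording at the EOS/ET visit. Protocol 9.2.2.3 does not require monitoring after end of study and sends SAEs from outside the reporting period to the safety database, which is not among the analysis data sources listed in SAP 9.2. Stopping product does not end the study either: Protocol 6.2.1.2 keeps undosed and partly dosed subjects on study, and 7.2.3 places their final visit 12 weeks after the dose. After withdrawal of consent, Protocol 8.1 permits only publicly available data. The SAE paragraph also sits under the TEAE heading, so a subset may have been intended.

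The rarity stands. The rest does not remove the point. Protocol 9.2.2.2 requires SAEs to 12 weeks after the dose through the Event CRF, and 9.2.2.3 accepts reports after end of study, so an SAE starting before Day 85 in a subject who has left can enter the study database. If a subset was intended, the SAE paragraph still states its own, longer window.

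A reader might also infer more than the documents support:

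- **That DREs are counted in one table and dropped from another.** DREs are a separate category and never enter the TEAE table. Their window merely differs from the TEAE window.
- **That deaths after early exit are lost.** A fatal AE is serious under Protocol 9.1.3 and stays in the uncut SAE window. A disease-related death is a DRE, also uncut. What is missing is a stated window for the fatal-AE table. The public-records search in Protocol 12.4 concerns survival status, not event terms or onset dates.
- **That the 5% dropout means about 3 of 54 subjects are affected** (0.05 × 54 = 2.7). That 5% is a sample-size allowance for an endpoint measured on Day 1, not a 12-week attrition rate. A leaver is affected only if a new SAE follows and is reported.
- **That early exit is probably exposure-related.** Nothing in the documents says so.

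**Conclusion.** The point holds as an internal inconsistency in the SAP with a small practical effect. TEAEs and SAEs have different upper limits, so the SAE table is not guaranteed to be a subset of the all-TEAE table. The exposed period is 85 minus the end-of-study day, and one affected subject with no other TEAE is worth about 3.7 points of TEAE incidence in an arm of 27.

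This rests on reading the TEAE clause as the earlier of two dates, which Appendix A supports, and on a post-exit SAE reaching the analysis data, which is possible but likely rare. The documents give no rate for such events, so no expected number can be calculated. The consequence is limited to the consistency of the safety tables.

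**What to change.** In SAP 6.5, state one upper limit for TEAEs and SAEs, apply it also to DREs and serious DREs, and say that the fatal-event tables use it.

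- **Preferred: delete the end-of-study clause from the TEAE definition**, so that all categories end 84 days after product. This matches the 12-week reporting period in Protocol 9.2.1 to 9.2.2.2 and keeps any SAE reported after early exit. The small downside is that non-serious events after exit are not actively collected, so that part of the window will be under-recorded. Add a sentence that data after withdrawal of consent remain limited by Protocol 8.1.
- **Also consistent: apply the Appendix A rule**, the earlier of end of study and 84 days after product, to every category. This fits Protocol 7.3.10, but it drops from the tables an SAE that was reported after early exit.

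Either way the cost is a few words in SAP 6.5 before database lock and a matching check of the event flags. No new data are needed.

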7.1 Full Analysis Set

The Full Analysis Set (FAS) includes all randomized subjects. Subjects will be analyzed according to their randomized treatment, regardless of the treatment received.

7.2 Safety Analysis Set

The Safety Analysis Set (SAS) includes all randomized subjects who received at least one dose of investigational product. For all safety analyses, subjects will be grouped according to the actual treatment received.

7.3 Efficacy Analysis Set

The Efficacy Analysis Set (EAS) utilizes the FAS and includes subjects who received IP and completed the exercise treadmill test post-randomization (ETTr). Subjects will be grouped according to their randomized treatment, regardless of the treatment received.

7.4 Per Protocol Set

The Per Protocol Set (PPS) utilizes the EAS and includes subjects who completed IP on Study Day 1 and do not have important protocol deviations that will potentially impact primary analysis of efficacy endpoints. Subjects who deviate from key eligibility criteria including currently participating in another investigational device or drug study (exclusion criteria 201) and cardiovascular conditions (exclusion criteria 214, 215, 216, 217, 218) will be excluded from the analysis.

7.5 Subgroup Analyses

Primary and secondary analyses will be performed according to the following subgroups: baseline TET (< 7 minutes or \geq 7 minutes) randomization strata, age group (<65, \geq 65) and sex.

8. Interim Analysis and Early Stopping Guidelines

A Data Monitoring Committee (DMC) will review all available safety data periodically. The DMC will have access to subjects' individual treatment assignments. To minimize the potential introduction of bias to the conduct of the study, members of the DMC will not have any direct contact with study center personnel or subjects. The DMC will communicate major safety concerns and recommendations regarding study modification or termination based on the safety parameters to Amgen in accordance with the DMC charter.

Records of all meetings will be maintained by the DMC for the duration of the study. Records of all meetings will be stored in the Amgen official document management system at the conclusion of the study. Further details are provided in the DMC charter.

No interim analysis is planned for this study except for sample size re-estimation that will be performed on the pooled sample after 45 subjects have been enrolled. Amgen may choose to alter the sample size based on the pooled variance in the overall group.

9. Data Screening and Acceptance

